### **5.1.3 Previous and Concomitant Treatment**

#### **5.1.3.1 Previous Medication**

Previous medications are any prescription or over-the-counter preparations, including herbal products and “natural remedies”, used by a subject prior to screening.

If not specified differently, intake of any medication within 4 months prior to randomization should be documented in the eCRF. The medication name, start and stop date, route, dose and frequency, and indication for each medication will be entered in the eCRF.

The last treatment course of any prior treatment received for anemia (medication or procedures such as ESAs, oral or IV iron, and RBC transfusions) within 12 months prior to randomization will be documented in the eCRF.

Certain prior medications are prohibited for a specified time frame prior and/or during the study treatment period and/or until EOS. These medications and restrictions are described in Section [5.1.3.3](#)

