3. Monthly IV iron use (mg) during weeks 1 to 36 will be compared (roxadustat versus ESA) using an MMRM method including BL Hb and other stratification factors as covariates. Superiority will be declared if the upper bound of the 2-sided  $100 \times (1 - \alpha^2)\%$  CI of the difference (roxadustat minus ESA) is lower than 0 mg.
4. Change from BL in PF subscore of SF-36 to the average of weeks 12–28 will be compared (roxadustat versus ESA) using an MMRM method including BL Hb value and other stratification factors as covariates. Non-inferiority can be concluded if the lower bound of the 2-sided  $100 \times (1 - \alpha^2)\%$  CI of the difference (roxadustat minus ESA) is greater than -3 points.
5. Change from BL in VT subscore of SF-36 to the average of weeks 12–28 will be compared (roxadustat versus ESA) using an MMRM method including BL Hb value and other stratification factors as covariates. Noninferiority can be concluded if the lower bound of the 2-sided  $100 \times (1 - \alpha^2)\%$  CI of the difference (roxadustat minus ESA) is greater than -3 points.
6. Change from BL in MAP to the average of weeks 20–28 will be compared (roxadustat versus ESA) using an MMRM including BL Hb value and other stratification factors as covariates. Noninferiority can be concluded if the upper bound of the 2-sided  $100 \times (1 - \alpha^2)\%$  CI of the difference (roxadustat minus ESA) is lower than 1 mmHg.
7. Time to an increase in blood pressure during weeks 1 to 36 will be compared (roxadustat relative to ESA) using a Cox Proportional Hazards regression analysis including BL Hb value and other stratification factors as covariates. Noninferiority will be declared if the upper bound of the 2-sided  $100 \times (1 - \alpha^2)\%$  CI of the hazard ratio (roxadustat relative to ESA) is lower than 1.3.
8. Change from BL in MAP to the average of weeks 20–28 will be compared (roxadustat versus ESA) using an MMRM method including BL Hb value and other stratification

factors as covariates. Superiority will be declared if the upper bound of the 2-sided  $100 \times (1 - \alpha * 2) \%$  CI of the difference (roxadustat minus ESA) is lower than 0 mmHg.

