Randomization will be stratified by region using two categories:

- Region A: Western Europe
- Region B: Central and Eastern Europe.

Time to Treatment Discontinuation

Time to Treatment Discontinuation in years is defined as:

Time to Treatment Discontinuation (years) = ('Date of Treatment Discontinuation' - 'Analysis date of first dose intake' + 1) / 365.25

In case a subject completed the treatment period, time to censoring will be calculated as:

$$(\text{EoT visit} - \text{Analysis date of first dose intake} + 1) / 365.25$$

Time in years from Diagnosis of Anemia

Time from diagnosis of anemia in years is defined as:

Time from Diagnosis of Anemia (years) = ('Analysis date of first dose intake' - 'Date of Diagnosis') / 365.25

In case of partial dates, imputation rules apply and are detailed in Section [7.11.2](#)

Time in years from Diagnosis of CKD

Time from diagnosis of CKD in years is defined as:

Time from Diagnosis of CKD (years) = ('Analysis date of First Dose intake' - 'Date of Diagnosis of CKD') / 365.25

In case of partial dates, imputation rules apply and are detailed in Section [7.11.2](#)

Time from Diagnosis of Targeted Medical History

Onset date and the start date of analysis for the study drug are collected and the time from diagnosis of targeted medical history in years is defined as

$$\text{Time from Diagnosis of Targeted Medical History (years)} = \frac{(\text{'Analysis date of first dose intake'} - \text{'Onset Date'})}{365.25}$$

In case of partial dates, imputation rules apply and are detailed in Section [7.11.2](#)

This will be calculated for each patient who was diagnosed with the targeted medical history: hypertension, diabetes mellitus type 1, type 2 and combined, dyslipidemia and vascular access.

Iron Repletion at Screening

Subjects will be classified in one of the following groups according to the TSAT and ferritin levels collected at Screening (prior to first drug intake):

- Ferritin <100 ng/mL and TSAT <20%
- Ferritin < 100 ng/mL and TSAT \geq 20%
- Ferritin \geq 100 ng/mL and TSAT <20%
- Ferritin \geq 100 ng/mL and TSAT \geq 20%
- Other

Iron Repletion at Baseline

Subjects will be classified in one of the following groups according to the TSAT and ferritin levels collected on Day 1:

- Ferritin <100 ng/mL and TSAT <20%
- Ferritin < 100 ng/mL and TSAT \geq 20%
- Ferritin \geq 100 ng/mL and TSAT <20%
- Ferritin \geq 100 ng/mL and TSAT \geq 20%
- Other

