7.4.2.2 Change from BL in Low Density Lipoprotein (LDL) cholesterol to the average LDL cholesterol of weeks 12 to 28.

LDL change from baseline to the average LDL value in weeks 12-28 will be compared by treatment arms using a MMRM model as in Section 7.4.1.1.1 (with the addition of LDL at baseline as a continuous covariate).

The analysis will be similar to the primary analysis provided in Section 7.4.1.1.1 except that it will be a superiority test instead of a non-inferiority test. This superiority test will be considered successful if the upper bound of the two-sided 95% confidence interval of the difference between treatment arms (roxadustat minus ESA) is lower than 0.

The analysis will be done on the FAS. An additional analysis (not part of the sequence) will be done on All Randomized.

For missing LDL imputation rules, refer to Section 7.11.1

Theses analyses will be done on all values (regardless of fasting status).

In addition to the inferential analysis, LDL cholesterol and LDL cholesterol change from baseline will be reported descriptively by visit for fasted values. The average of weeks 12-28 will also be reported.

Residual plots will be produced showing the following:

- Model residuals in the y-axis and model predictions in the x-axis,
- Model residuals in the y-axis and baseline LDL-cholesterol in the x-axis.

Table 19 Primary and Sensitivity Analysis for Change from BL in LDL to the Average LDL of weeks 12 to 28

Code	Set	Endpoint	Method	Covariates
Primary	FAS	Change from BL in Low Density Lipoprotein (LDL) cholesterol to the average LDL cholesterol of weeks 12 to 28.	MMRM	Region, History of CV, Previous ESA treatment, Visits and Visit by Treatment, BL Hb, BL LDL
S1	All Randomized	Change from BL in Low Density Lipoprotein (LDL) cholesterol to the average LDL cholesterol of weeks 12 to 28.	MMRM	Region, History of CV, Previous ESA treatment, Visits and Visit by Treatment, BL Hb, BL LDL

7.4.2.3 Mean monthly IV iron use (mg) during Day 1 to Week 36 (monthly defined as a period of 4 weeks).

The average monthly IV iron use (mg) during Day 1 to Week 36 will be compared by treatment arm using an ANCOVA model, as in Section 7.4.1.2.1 (except that it will be done on the total average of weeks 1 to 36 and that there will be no imputation). Subjects on study with no medication record of IV Iron will be assumed that they received no IV Iron. For those subjects (on study), monthly IV iron use will be set to zero mg.

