The analysis will be done on the FAS. This superiority test will be considered successful if the upper bound of the two-sided 95% confidence interval of the difference between treatment arms (roxadustat minus ESA) is lower than 0.

An additional analysis (not part of the sequence) will be performed on All Randomized.

Furthermore, the mean monthly IV iron use will be reported for Day 1 to Week 36, weeks 37 to 52, and weeks 53 to 104. Number and percentage of subjects took IV iron and/or Oral Iron at any time and during Day 1 to week 36, weeks 37 to 52, and weeks 53 to 104 will be summarized.

Time to first IV iron during day 1 to week 36 will be analyzed similarly as in Section 7.4.2.7

Table 20 Primary and Sensitivity Analysis for Mean Monthly IV Iron use (mg) During Day 1 to Week 36

Code	Set	Endpoint	Method	Covariates
Primary	FAS	Mean monthly IV iron use (mg) during Day 1 to Week 36	ANCOVA	Region, History of CV, Previous ESA treatment, BL Hb
S1	All Randomized	Mean monthly IV iron use (mg) during Day 1 to Week 36	ANCOVA	Region, History of CV, Previous ESA treatment, BL Hb
S2	FAS	Occurrence and time to first use of IV iron in day 1 to week 36	Cox regression + Kaplan Meier	Stratified on Region, History of CV, Previous ESA treatment, and adjusted on BL Hb as continuous covariate

7.4.2.4 Change from BL in SF-36 Physical Functioning (PF) sub-score to the average PF sub-score of weeks 12 to 28.

Change from baseline in PF subscore of SF-36 to the average of weeks 12–28 will be compared by treatment arm, for the PPS. It will be done using a MMRM method using region, history of CV, previous ESA treatment as categorical covariates and baseline SF-36 PF subscore, baseline Hb as continuous covariates. Non-inferiority can be concluded if the lower bound of the two-sided 95% CI of the difference between the two treatment arms (roxadustat minus ESA) is greater than -3 points.

The analysis will be similar to the one provided in Section [7.4.1.1.1](#)

Residual plots will be produced showing the following:

- Model residuals in the y-axis and model predictions in the x-axis,
- Model residuals in the y-axis and baseline SF-36 PF subscore in the x-axis.

An additional analysis (not part of the sequence) will be done on All Randomized.

The analysis will be repeated in the subsets of subjects with baseline PF subscore below 40 and equal or above 40.

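### The IV iron comparison (key secondary Test 3) adjusts for baseline Hb but for no baseline iron measure, although ferritin, TSAT and prior IV iron are already collected

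*SAP*

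**What the plan says.** SAP 7.4.2.3 states: "The average monthly IV iron use (mg) during Day 1 to Week 36 will be compared by treatment arm using an ANCOVA model". The form is that of the US primary ANCOVA, without imputation. SAP Table 20 lists the covariates as "Region, History of CV, Previous ESA treatment, BL Hb", for the FAS primary analysis and the All Randomized repeat alike. Superiority is claimed if the "upper bound of the two-sided 95% confidence interval of the difference between treatment arms (roxadustat minus ESA) is lower than 0". Protocol 7.4.2.1 had planned this test "using an MMRM method including BL Hb and other stratification factors as covariates", so it names no iron covariate either. The SAP revision history (version 2.0, item 22) records the move from MMRM to ANCOVA because of the data distribution.

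Other key secondary models treat baseline differently. The LDL model is run "with the addition of LDL at baseline as a continuous covariate", and the SF-36 PF, SF-36 VT and MAP models (SAP 7.4.2.4 to 7.4.2.6) likewise add the baseline of their own endpoint. The blood-pressure Cox models (SAP Table 24) adjust for baseline Hb and not for baseline blood pressure.

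The iron data exist. The Schedule of Assessments takes ferritin and TSAT at screening and on Day 1. SAP 6.5.2 says: "Subjects will be classified in one of the following groups according to the TSAT and ferritin levels collected on Day 1", with the screening classification as fallback. SAP 7.2.3 only tabulates the result. For prior treatment, protocol 5.1.3.1 has the eCRF record "The last treatment course of any prior treatment received for anemia (medication or procedures such as ESAs, oral or IV iron, and RBC transfusions", looking back 12 months, and also says that "intake of any medication within 4 months prior to randomization should be documented in the eCRF", with route and dose.

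**The concern.** Baseline Hb is the natural covariate in the Hb model from which the Test 3 ANCOVA is borrowed. Carried over to IV iron, the same list leaves a model with nothing in it about iron. Iron status and recent IV iron are the obvious candidates to predict later IV iron use, and they are measured before randomization.

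Nothing else in the plan covers them. None of the five stratification factors (SAP 3.3) concerns iron, and baseline iron is not among the subgroups in SAP 7.8. The provision for extra adjustment after a baseline imbalance (SAP 7.4.1.1.2, 7.4.1.2.1 and 7.4.1.2.2) is optional and covers the primary endpoints only.

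Test 3 is third of nine in a fixed sequence, so if it fails, Tests 4 to 9 cannot be claimed. Precision in this test therefore matters beyond the IV iron claim itself.

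**Working it through.** **What the plan gives.** SAP section 4 powers only the two primary Hb endpoints. Its EU figure reproduces for the overall population: SE = 1.5 × √(2/300) = 0.1225 g/dL; distance from margin 0.75 − 0.25 = 0.5; 0.5/0.1225 = 4.08; less 2.11 (one-sided 0.0174) = 1.97, which gives 97.6% against the stated 97%. That calculation supplies nothing for IV iron. No SD, effect, power or covariate correlation is stated for Test 3, so what follows rests on an assumed range.

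**Inputs.** ρ is the partial correlation of the baseline iron covariates, taken together, with mean monthly IV iron, given the planned covariates. Assumed range: 0.1 to 0.4. Allocation is 1:1 and the test level is one-sided 0.025.

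**Formulas.**
- Precision: adjustment multiplies the SE by √(1 − ρ²).
- Power, for a test that has 80% without adjustment: Φ[(1.96 + 0.84)/√(1 − ρ²) − 1.96].
- Chance imbalance: the standardized difference in baseline iron between arms has SD √(2/n), so its 95% range is ±1.96 × √(2/375) = ±0.14 SD with 375 per arm, or ±0.16 SD with 300 per arm. At that edge the estimate without an iron covariate moves by ρ × 1.96 × √(2/n) outcome SDs. Its SE is √(2/n) outcome SDs, so the move is 1.96ρ standard errors.
- One-sided error, given an imbalance at that edge in roxadustat's favour: 1 − Φ[(1.96 − 1.96ρ)/√(1 − ρ²)].

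| ρ (assumed) | SE reduction | 80% power becomes | Shift at the 95% edge | Conditional one-sided error |
|---|---|---|---|---|
| 0.1 | 0.5% | 80.4% | 0.20 SE | 0.038 |
| 0.2 | 2.0% | 81.6% | 0.39 SE | 0.055 |
| 0.3 | 4.6% | 83.6% | 0.59 SE | 0.075 |
| 0.4 | 8.3% | 86.4% | 0.78 SE | 0.100 |

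The precision and imbalance columns describe the same share of variance, ρ², in two ways and should not be added. An imbalance of the same size in the other direction lowers the error (to 0.015 at ρ = 0.1 and 0.001 at ρ = 0.4). Averaged over randomizations the level stays at 0.025.

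**Check with many zeros.** The formulas assume a well-behaved outcome, so the test was also simulated: 350 per arm, 3,000 runs, gamma-distributed amounts among users, and a probability of use at the covariate mean of 1/(1 + e^0.4) = 0.40. With baseline correlations of 0.15, 0.28 and 0.40, the SE ratio with adjustment was 0.990, 0.962 and 0.916, so cuts of about 1%, 4% and 8%. The null rejection rate was about 0.03 with and without adjustment (Monte Carlo SE about 0.003).

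**The case against.** The strongest reply is that the planned test is valid, agrees with the protocol, and omits a prognostic variable as any randomized comparison may. That is correct. A reader might infer bias, an inflated type I error or a protocol-SAP conflict. The documents support none of these: randomization protects the level on average, and the protocol names no iron covariate.

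The comparison with other models is also limited. LDL, SF-36 and MAP are change scores whose baseline is part of the outcome. Monthly IV iron is not a change score, and ferritin is not its baseline. The blood-pressure Cox models omit their own baseline too. So the SAP is not breaking a rule that it follows everywhere else.

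The link between baseline iron and later IV iron may be weak. A reader might take ferritin below 100 ng/mL or TSAT below 20% as the sole protocol condition for IV iron. Protocol 5.1.3.2 does not say that. On roxadustat it first requires an inadequate Hb response after dose increases or arrival at the maximum dose, and oral iron intolerance can stand in for low iron values. All of this concerns status during treatment. On ESA, IV iron follows standard of care. Entry at ferritin of at least 100 ng/mL and TSAT of at least 20% cuts off the low end of both predictors, although no upper limit is set. The SAP revision history (version 3.0, item 5) notes that most subjects used no IV iron. These points argue for a small gain. They do not argue against adjusting: with 1:1 allocation, a common slope that fits the arms unequally reduces the benefit without harming the comparison.

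Timing is a fair worry. SAP 3.0 is dated 10 September 2018, the study is open-label, and some covariate decisions already followed data review. A late change to a confirmatory model could look data-driven, which is why the fix must be specified without reference to outcome by arm.

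**Conclusion.** The point holds as a low-cost improvement to a valid test. The Test 3 ANCOVA leaves out baseline iron information that the trial already collects. It thereby gives up some precision, and protection against chance imbalance, in a test on which six later tests depend.

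The size is an assumption: an SE reduction of about 0.5% to 8% for a partial correlation of 0.1 to 0.4, with the low end likelier. A reader might infer something larger, such as a gain worth a quarter more subjects. That needs 1/(1 − ρ²) = 1.25, so ρ² = 0.20 and ρ of about 0.45 beyond region, ESA type and Hb, and nothing in the documents supports such a value. Nor do they show that a few percent of interval width would decide whether Tests 4 to 9 are reached.

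The conclusion covers the linear ANCOVA only. A reader might extend it to the time-to-first-IV-iron Cox analysis (S2 in Table 20). The √(1 − ρ²) argument does not carry over: adding prognostic covariates to a Cox model changes the conditional hazard ratio being estimated and does not in general shrink its SE.

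**What to change.** Before database hard lock, up to which SAP section 1 allows revisions, add three covariates to the Test 3 ANCOVA on the FAS and to its All Randomized repeat:

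- Day 1 log-ferritin, with the screening value if Day 1 is missing;
- Day 1 TSAT, with the same fallback;
- prior IV iron, defined in the SAP, for example yes/no from the anemia treatment history and the prior medication records, with the look-back period stated.

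Keep the current four-covariate model as a sensitivity run, and leave the S2 Cox model as it is. State whether the analyses that borrow this model (Table 25 row A3, and the later IV iron periods in SAP 7.4.3.8) follow the change.

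The cost is SAP wording, about three degrees of freedom and one new derivation, since the SAP defines no prior IV iron variable. No new data are needed. The covariates and their coding must be fixed without reference to outcome by arm, and the revision history should say so.

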7.4.2.7 Time to first occurrence of an increase in pre-dialysis blood pressure: An increase from BL of ≥ 20 mm Hg systolic blood pressure (SBP) and $SBP \geq 170$ mmHg or an increase from baseline of ≥ 15 mmHg diastolic blood pressure (DBP) and $DBP \geq 100$ mmHg during weeks 1 to 36.

Time to first occurrence of an increase in blood pressure during the first 36 weeks, including time to censoring, defined in Section 6.1.2.7 will be used in a Cox Proportional Hazards regression analysis. It will compare treatment arms, using covariates defined in Section 7.4.1.1.1 and provide hazard ratio and their 95% confidence intervals.

Blood pressures are pre-dialysis blood pressures.

Non-inferiority will be declared if the upper bound of the 2-sided 95% confidence interval of the hazard ratio (roxadustat as relative to ESA), calculated on the PPS, is lower than 1.3. As per Table 17, once the null hypothesis is rejected, superiority will be checked for this variable on the FAS, as part of the fixed sequence testing procedure. Superiority will be concluded if the upper bound of the two-sided 95% CI of the hazard ratio of the two treatment arms (roxadustat as relative to ESA) is lower than 1.

A sensitivity analysis will be done on All Randomized.

The Cox Model can be written:

$$\lambda_j(t; \underline{x}) = \lambda_{0j}(t) \exp(z)$$

where

j - indicator for stratum

z – treatment indicator – which is either roxadustat or ESA

The SAS procedure for the Cox regression will be similar to the following:

```
proc phreg;  
  model time_to_event*cens_var(1) = treatment Hb_base / rl;  
  strata previous_ESA_treatment region cv_history;  
where visit in  
  ('Day1', 'Week1', 'Week2', ..., 'Week8', 'Week10', ..., 'Week36');  
run;
```

In addition, the cumulative incidence curve of subjects with an increase in blood pressure from baseline will be plotted by treatment arm and type of ESA treatment.

The cumulative incidence will be calculated as one minus the Kaplan-Meier estimate of the survival function. Two types of analyses can be performed: modeling the cause specific hazard or modeling the hazard of the sub-distribution. The first approach has been chosen in this SAP, because competing risks are assumed not to exist, since the main interest is to study the treatments effect and this method provides results to be generalized across datasets with different competing risks. One minus the Kaplan-Meier estimate can be interpreted as the probability that an event of interest occurs to a subject by time t, in the absence of any competing risk.

In addition to the cumulative incidence plot, the cumulative incidence at 0.25, 0.5 and 0.75 year with the 95% confidence interval will be reported using Greenwood’s formula.

Model checking

The proportional hazards assumption will be checked graphically using a log-cumulative hazard plot against log-survival time. This plot will give approximately parallel lines if the proportional hazards assumption between treatment arms subgroups holds.

The proportional hazards assumption will also be tested by fitting a Cox Proportional Hazards regression, stratified for region, history of CV, previous ESA treatment, and adjusted for baseline Hb (continuous) with one dependent variable: treatment (0 for ESA, 1 for roxadustat).

Table 24 Primary and Sensitivity Analysis for the time to First Occurrence of an Increase in Blood Pressure in the First 36 weeks

Code	Set	Endpoint	Method	Strata/Covariates
Primary	PPS	Occurrence and time to first occurrence of increase in blood pressure in week 1 to 36	Cox regression + Kaplan Meier	Stratified on Region, History of CV, Previous ESA treatment, and adjusted on BL Hb as continuous covariate
Primary	FAS	Occurrence and time to occurrence of increase in blood pressure in week 1 to 36	Cox regression+ Kaplan Meier	Stratified on Region, History of CV, Previous ESA treatment, and adjusted on BL Hb as continuous covariate
S1	All Randomized	Occurrence and time to occurrence of increase in blood pressure in week 1 to 36	Cox regression+ Kaplan Meier	Stratified on Region, History of CV, Previous ESA treatment, and adjusted on BL Hb as continuous covariate

In addition, the number and percentage of subjects with an increase from baseline in blood pressure during weeks 1 to 36 will be reported by treatment arm and type of ESA treatment, on the PPS. They will also be reported for the total duration of the study. For subjects who have experienced more than one increase in blood pressure, only their first event following study treatment will be used in the analysis.

In addition, the incidence rate (per 100 subject years at risk) will also be calculated as follows:

$$\frac{\text{Number of subjects with event}}{\text{Total cumulative time at risk (years)}} \times 100$$

Where Total cumulative time at risk is the sum of individual time at risk defined as either time to occurrence of the event or time to censoring for subjects with no event.

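### The planned test of proportional hazards in SAP 7.4.2.7 is the primary Cox model again, so it tests HR = 1 and not proportionality

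*SAP*

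**What the plan says.** SAP 7.4.2.7 analyzes time to first increase in pre-dialysis blood pressure over weeks 1 to 36 with a Cox model. The example code has the model statement "model time_to_event*cens_var(1) = treatment Hb_base / rl" and the strata statement "strata previous_ESA_treatment region cv_history". Table 24 gives the same specification in words: "Stratified on Region, History of CV, Previous ESA treatment, and adjusted on BL Hb as continuous covariate".

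Two decisions are read from the resulting hazard ratio. Test 7 declares non-inferiority if the upper limit of the two-sided 95% confidence interval, "calculated on the PPS, is lower than 1.3". Test 9 declares superiority if the upper limit on the FAS is below 1.

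The model-checking paragraph of the same section plans two checks:

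- A graph: "The proportional hazards assumption will be checked graphically using a log-cumulative hazard plot against log-survival time".
- A formal test: "The proportional hazards assumption will also be tested by fitting a Cox Proportional Hazards regression". This model is stratified for region, cardiovascular history and previous ESA, and is "adjusted for baseline Hb (continuous) with one dependent variable: treatment (0 for ESA, 1 for roxadustat".

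Neither the SAP nor the protocol names a treatment-by-time term, a residual-based test or any other formal test of proportionality. Neither says what follows if the assumption appears to fail.

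**The concern.** A Cox model with one constant treatment coefficient assumes proportional hazards, so its own treatment p-value cannot be evidence for or against that assumption. If the sentence is programmed as written, the output labelled as the proportionality test will be the primary treatment comparison under another name.

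The design gives some reason to want a working check. One arm changes drug on day 1 while the other continues ESA at about the same weekly dose (Protocol 2.2.1.3), and the roxadustat dose is held for four weeks and then titrated (Protocol synopsis, Doses). A hazard ratio that differs between the early weeks and later ones is plausible, though the documents hold no data on it.

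If the ratio does change, the single Cox estimate is an average whose weights depend on when events and censoring occur. A confidence limit below 1.3 would then not show that the ratio stays below 1.3 throughout the 36 weeks. That is a matter of interpreting Test 7, which is also the gate to Tests 8 and 9 in the fixed sequence (SAP Table 17).

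**Working it through.** The plan states no figure to reproduce here. The check is a comparison of models, followed by a simulation of what the described test responds to.

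**Step 1. The two models side by side.**

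| Component | Primary model (SAP 7.4.2.7 code, Table 24) | Checking model (SAP 7.4.2.7, model checking) |
|---|---|---|
| Strata | previous ESA, region, CV history | region, CV history, previous ESA |
| Covariate | baseline Hb, continuous | baseline Hb, continuous |
| Treatment | one term | one term, coded 0/1 |
| Term in time | none | none |

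The checking text calls treatment the dependent variable. It can only be meant as the explanatory variable. The two models are the same.

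**Step 2. What each model can test.** In stratum s, with treatment z, both models are

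h(t) = h0s(t) exp(b z + g Hb).

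The only treatment hypothesis is b = 0, that is HR = 1. A test of proportionality needs a parameter for change over time, for example

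h(t) = h0s(t) exp(b z + d z log t + g Hb), with H0: d = 0.

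The SAP model fixes d at 0, so the test of its treatment coefficient says nothing about d.

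**Step 3. Simulation.** From the documents: about 600 subjects in the PPS, 300 per arm (SAP 4); three two-level strata, giving 2 x 2 x 2 = 8 cells; a baseline Hb covariate; 36 weeks. Assumed, because the documents give no event rate for this endpoint: 36-week ESA-arm risk of 15% or 30%, about 12% censoring, and the hazard-ratio patterns below. In the crossing patterns the ratio changes at week 18. There were 400 runs per row, with two-sided 5% tests. The largest Monte Carlo standard error is sqrt(0.5 x 0.5 / 400) = 2.5 percentage points.

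| ESA-arm risk | True HR | Mean events | SAP check rejects (b = 0) | Treatment x log(time) rejects (d = 0) |
|---|---|---|---|---|
| 15% | 1.0 constant | 85 | 5.8% | 4.0% |
| 15% | 0.6 constant | 69 | 52.0% | 2.8% |
| 15% | 0.5 constant | 65 | 76.2% | 3.3% |
| 15% | 0.5 then 1.9 | 92 | 12.2% | 54.2% |
| 15% | 0.4 then 1.75 | 87 | 6.5% | 64.0% |
| 30% | 1.0 constant | 171 | 6.0% | 4.0% |
| 30% | 0.6 constant | 140 | 84.8% | 5.2% |
| 30% | 0.5 constant | 132 | 97.3% | 4.8% |
| 30% | 0.5 then 1.9 | 182 | 11.0% | 90.5% |
| 30% | 0.4 then 1.75 | 175 | 5.5% | 89.7% |

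The SAP check follows the average treatment effect. It rejects often when hazards are proportional and the drug has an effect, and seldom when hazards cross and the effects roughly cancel. The interaction test stays near or below 5% in every proportional scenario and rises when the ratio changes.

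**The case against.** Several objections carry weight.

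- **Other displays exist.** A reader might infer that the plan has no way of seeing non-proportionality. That is not so. Besides the log-cumulative-hazard plot, SAP 7.4.2.7 plans cumulative incidence curves, and estimates at 0.25, 0.5 and 0.75 year with confidence intervals. The 0.25-year estimate falls at about week 13 (0.25 x 365.25 / 7 = 13.0), where an early blood pressure rise after the switch could show. These are descriptive displays, not tests, but they stand.
- **No pass/fail rule.** A reader might infer that a violation would be reported as tested and passed. The SAP gives no criterion and no reporting text for the check, so this cannot be concluded. The opposite error is equally open: a true effect under proportional hazards could be taken for a violation.
- **Test 9 is largely unaffected.** A reader might infer that both tests are compromised. Equal hazards are proportional, so the type I error of Test 9 under that null does not depend on this check. Its interpretation and power may. The decision rules of both tests use the confidence limit, not the outcome of the model check.
- **Reach to other endpoints.** Time to first IV iron, hospitalization, rescue therapy and others are analyzed similarly to this section. Whether the model-checking paragraph goes with them is inference.
- **Probable slip.** The misuse of the term dependent variable suggests that a time-interaction phrase was dropped. That is plausible but cannot be confirmed, and the text as it stands is what would be programmed.
- **Limits of the simulation.** The event risks are assumed, and the crossing patterns are strong ones chosen so that the effects roughly cancel. Even then the interaction test detects only 54% to 64% at the lower risk.

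None of this makes the described model a test of proportionality.

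**Conclusion.** The point holds in a limited form. The formal check in SAP 7.4.2.7 repeats the primary Cox model and answers the wrong question. This follows from the model specification and needs no assumption. The rejection rates of 52% to 97% under exact proportionality (hazard ratio 0.6 or 0.5) and 5.5% to 12.2% under crossing hazards illustrate the two directions of error. Those figures do depend on the assumed event risks, censoring and hazard patterns.

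The practical consequence is mainly for how the Test 7 hazard ratio is interpreted against its margin of 1.3. The documents do not show that hazards are in fact non-proportional, or that either test's decision rule is invalid. This is a minor correction, worth making because it is nearly free.

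**What to change.** Replace the sentence on the formal test with a prespecified one: add a treatment x log(time) term to the primary Cox model and test its coefficient, or use a scaled Schoenfeld residual test for treatment. If the interaction is chosen, define it inside the Cox procedure so that it is evaluated at each event time. It should not be computed beforehand from each subject's own follow-up time.

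State that the result is used for interpretation only. The hazard ratio and confidence limit for Tests 7 and 9 still come from the model without the added term, and their decision rules do not change. Keep the plot and the cumulative incidence displays.

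Period-specific hazard ratios may be added as supportive output, with the cut point fixed in advance; the documents offer no basis for a particular week. The later-period ratio covers only subjects still event-free, so it is not a clean randomized comparison.

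State whether the same check applies to the endpoints that refer back to this section.

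The cost is one or two sentences and a few lines of code, with no new data and no change to sample size or alpha. SAP 1 allows version-controlled revisions before database hard lock. After that, the change can be justified in the clinical study report.
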